2.2 Primary Objective

The primary objective is to evaluate the physiological impact of AIR+ KN95 Masks on end-tidal carbon dioxide (ETCO2) of children aged 7 to 14 years of age.

2.3. Secondary Objectives

The secondary outcomes include other physiological parameters such as oxygen saturation (SPO2), heart rate (HR) and respiratory rate (RR). In addition, we will assess the general well-being and comfort level of the child when wearing the AIR+ KN95 Mask.

2.4. Potential Risks and benefits:

a. End Points - Efficacy

There is no direct benefit in participating in this research. However, the knowledge gained would benefit other children and the public in the future. The results from this research will enable us to test the safety of the use of Air+ KN95 masks in children. This study will measure the carbon dioxide levels inside the mask and in the children as they wear it.

b. End Points - Safety

The study is designed to observe the impact of wearing the Air+ KN95 mask in children while at rest and on minimal exertion only. They may experience mild discomfort when wearing the mask whilst brisk walking on the treadmill. However, their vital signs will be monitored, and they will be encouraged to remove the mask if they feel uncomfortable.

Studies have shown that prolonged wearing of disposable particulate respirators may lead to an increase in carbon dioxide (CO2) levels which may result in headaches, increased irritability, or breathing discomfort. Usually, this is resolved by simply removing the mask.

3. STUDY POPULATION

3.1. List the number of subjects to be enrolled.

A total of 100 children will be recruited. Students aged 7 to 14 years old from two schools in Singapore [to be advised by MOE] will be invited to participate in this study. The participants will be randomly selected from the pool of qualifying subjects.

3.2. Criteria for Recruitment

Students aged 7 to 14 years old from schools as selected by MOE will be invited to participate in this study. Since subjects are minors, one of the parent or legal guardians will sign the informed consent form. There will be no restrictions based on race or gender. The subject must satisfy the inclusion and exclusion criteria to be eligible for the study. A Parental Screening Form will be attached to the **PARTICIPATION INFORMATION SHEET AND CONSENT FORM** for the parent or legal guardian to declare any past medical

condition(s) of the subject. Should parents have doubts about any of the questions in the Parental Screening Form, they will be able to contact the PI directly. Similarly, should the study team wish to clarify their concerns regarding parents' responses to the screening form prior to enrolling the subject, they will contact the parent directly. Any such communication between parent/legal guardian and PI will be documented in the study record.

3.3. Inclusion Criteria

The inclusion criteria are as follows:

1. Aged between 7 and 14 years of age (inclusive)
2. Subjects and their parents or legal guardian must provide their consent/ assent to take part in this study

3.4. Exclusion Criteria

The exclusion criteria are as follows:

[figure not shown]
1. Subjects with any known cardiorespiratory conditions (including but not limited to the following: asthma, bronchitis, cystic fibrosis, congenital heart disease, emphysema)
2. Subjects with any known medical conditions that may be exacerbated by strenuous activity, including but not limited to the following: exercise-induced asthma, lower respiratory infection (including pneumonia, bronchitis) in the past 2 weeks, anxiety disorders, diabetes, hypertension, or epilepsy/ seizure disorder
3. Subjects with any physical disability from medical, orthopaedic, or neuromuscular disorders
4. Subjects who have an acute upper respiratory tract infection/ moderately severe rhinitis (i.e. blocked nasal passages) on the day of the study
5. Subjects who may compromise the integrity of the mask fit (e.g. those with excessive facial hair)

3.5. Withdrawal Criteria

Subjects may withdraw voluntarily from participation in the study at any time.

Also, subject will be withdrawn from the study if there is clinical suspicion of hypercarbia or the physiological parameters exceed their threshold:

- ETCO₂ > 50mmHg for at least 3 minutes sustained
- SPO₂ < 92%
- HR and RR within 2.5 and 97.5 centiles by age as proposed by Wallis LA *et al*:

- Subject complains of symptoms such as dizziness & confusion, even if ETCO₂ or SPO₂ levels remain within the specified normal range i.e., ETCO₂ \leq 50mmHg and SPO₂ \geq 92%

3.6. Subject Replacement

Subjects who drop out will be replaced.

5. STUDY DESIGN

5.1. Summary of Study Design

This study is designed to explore and determine whether the new disposable particulate respirator is safe and effective for use in healthy children aged 7 to 14 years of age.

Figure 1 shows the algorithm of the summary design.

[figure not shown]

Figure 1. Study Design

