Studies have shown that prolonged wearing of disposable particulate respirators may lead to an increase in carbon dioxide (CO₂) levels in the dead space of the respirator as well as in the re-breathing of the expired air when wearing it. The increased CO₂ levels may result in headaches, increased irritability, and breathing difficulty. In addition, there is some discomfort due to the accumulation of heat and humid air in the dead space of between the respirator and face. However, the mask design is based on our previous AIR+ Smart Mask specifications, which was previously evaluated in a clinical trial performed in collaboration with NUH and the data published in a peer-reviewed journal¹, showing no significant increase in CO₂ retention and the mask was found to be comfortable at rest and on mild exertion. The mask was commercially launched in 2015.

As the masks were developed specifically for school-going children, this study is designed to explore whether the new disposable particulate respirator is safe and effective for use in healthy children aged 7 to 14 years of age. This is through measuring the variation of carbon dioxide levels in children whilst wearing the AIR+ KN95 Mask. End-tidal carbon dioxide pressure (ETCO2) is a good indicator of arterial carbon dioxide pressure (PaCO2) in healthy adults and children and has been used for continuous direct assessment of PaCO2 in clinical contexts. The normal range of PaCO2 is from 35 – 45 mmHg. As there is a slight margin of difference between ETCO2 and PaCO2 values during measurement of about 1.6 +/- 4.3mmHg, this study defines 30 to 50mmHg as the acceptable range for ETCO2 levels.

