6. METHODS AND ASSESSMENTS

6.1. Selection of Test Subjects

a. Screening Visit and Procedures

Pre-test actions

An invitation letter with study information sheet which contains the study's objectives, procedures, risk and benefits will be sent to all subjects aged 7 to 14 years old from the selected schools. Their parents will complete a questionnaire to ascertain the students' general well-being, and to ensure that the appropriate criteria for selection / exclusion are applied. Contact of the designated study team member will be provided for any queries.

Subjects who fulfil the eligibility criteria, whose parents return the Reply form expressing their willingness to participate, will proceed on to the study enrolment.

The total number of eligible students may exceed the stated sample size, in which case the participants will be randomly selected from the pool of qualifying subjects.

b. Study Visit and Procedures

On-site pre-screening

An on-site screening questionnaire will be administered by the study team to check on the participant's current well-being. Informed consent and/or assent if applicable will be obtained.

Mask fit test

Biometric data (gender, age, race, height, and weight) of the subjects will be recorded. De-identified case report form will be used to record data. Each will then undergo a mask fit test to determine the right mask size for the face, and test for leakage by performing the following exercises in sequence, which would take 12 minutes each: normal breathing, deep breathing, turning their heads sideways, up and down, speaking and bending exercise. The fit test will be performed using the Portacount Respirator Fit Tester which indicates the fit factor (ratio of ambient air particle concentration vs. in-mask particle concentrations). A high fit factor will indicate a good seal, and the passing fit factor is 12.5 (8% leakage) based on respirator certification EN 149:2001+A1:2009 FFP2 standards. Should a subject keep failing the fit test despite trying on all the sizes, they will be excluded from the study.

The study

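### The stated aim includes effectiveness, but the fit factor, the only in-child measure of protection, serves only for sizing and entry and is never analysed

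*Combined protocol and SAP*

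**What the plan says.** Section 5.1 says the study is to explore and determine "whether the new disposable particulate respirator is safe and effective for use in healthy children". Sections 1.1 and 1.2 c state the same aim, with the weaker verb of exploring. The rationale in 1.1 and 1.2 c is about fit: masks made for adults sit poorly on children's faces, and 1.1 adds that they therefore protect poorly against PM2.5.

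On how the aim is to be met, 1.1 says: "This is through measuring the variation of carbon dioxide levels in children whilst wearing the AIR+ KN95 Mask". The hypothesis (2.1) and primary objective (2.2) concern ETCO2. Section 2.3 adds SPO2, heart rate, respiratory rate, well-being and comfort. The paragraph in 2.4 a, which carries an efficacy heading, names no efficacy endpoint and says instead: "The results from this research will enable us to test the safety of the use of Air+ KN95 masks in children".

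Section 6.1 b describes a quantitative fit test with a pass mark of 12.5, equated with 8% leakage. It serves to find the right size and to check for leakage. On failures it says: "Should a subject keep failing the fit test despite trying on all the sizes, they will be excluded from the study". Section 4 says the same.

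Section 11.2 plans analyses of ETCO2, SPO2, heart rate, respiratory rate and the visual analogue scale. Fit factor, pass proportion and number of fit failures do not appear.

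**The concern.** Fit is the protocol's own reason for developing a children's mask, and effectiveness is named in the aim three times. Yet every planned outcome concerns physiology or comfort. CO2 retention tells us about the safety of wearing the mask, not about how much particulate it keeps out.

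Two things are at stake. First, a favourable ETCO2 result could be reported under a safe-and-effective aim with no result on fit behind the second word. Second, children whom no size fits are removed before the ETCO2 test, so the ETCO2 finding describes only fitted children. The plan neither says so nor commits to reporting what share of tested children that is.

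**Working it through.** **Step 1. Set aim, outcomes and analysis side by side.**

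| Item | Where | Safety or comfort | Fit or protection |
|---|---|---|---|
| Narrative aim | 1.1, 1.2 c, 5.1 | yes | yes |
| Hypothesis, primary objective | 2.1, 2.2 | ETCO2 | none |
| Secondary objectives | 2.3 | SPO2, HR, RR, well-being, comfort | none |
| Paragraph headed as efficacy | 2.4 a | safety | none |
| Measurement | 6.1 b | ETCO2, SPO2, HR, RR, VAS | fit factor |
| Sample size | 11.1 | ETCO2 | none |
| Analysis | 11.2 | ETCO2, SPO2, HR, RR, VAS | none |

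The fit factor is measured but enters no objective and no analysis.

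**Step 2. Reproduce the plan's figure.** The fit factor is the ratio of ambient to in-mask particle concentration (6.1 b), so leakage = 1 / fit factor = 1 / 12.5 = 0.08, or 8%. This agrees with the protocol.

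**Step 3. Consequence of the gate.** A child reaches the ETCO2 test only after passing. Among children analysed for ETCO2 the pass rate is therefore 100% by construction and says nothing about the pass rate among those tested.

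**Step 4. What a reported pass proportion would show.** The documents give no pass rate, so the rates below are assumptions. For x passes among n tested, the exact (Clopper-Pearson) 95% limits are

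- lower = 0.025 quantile of Beta(x, n − x + 1)
- upper = 0.975 quantile of Beta(x + 1, n − x)

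With n = 100 tested:

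| Assumed passes | Exact 95% CI |
|---|---|
| 95 | 88.7–98.4% |
| 90 | 82.4–95.1% |
| 80 | 70.8–87.3% |
| 70 | 60.0–78.8% |

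**Step 5. What the 100 refers to.** Sections 3.1 and 11.1 say 100 children are recruited. Section 6.1 b places consent before the fit test, and 3.6 replaces drop-outs without saying whether a fit failure is one. Two readings are open:

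- Failures count towards the 100 and are not replaced. Then 100 × 0.95 = 95 or 100 × 0.80 = 80 children go on to the ETCO2 test.
- The 100 are fitted children. Then 100 / 0.95, rounded up to 106, or 100 / 0.80 = 125 must be tested. For 100 passes among 125 the exact interval is 71.9–86.6%, treating the number tested as fixed.

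Under either reading the interval is narrow enough to be useful.

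**The case against.** The strongest reply is that the formal question is narrower than the narrative. The hypothesis and objectives are about ETCO2, other vital signs and comfort. Section 1.1 says the aim is met through CO2 measurement, and 11.2 analyses what section 2 lists. On that view the defect is loose wording. This stands in part: a reader might infer that a planned effectiveness objective was left without its analysis, but section 2 contains no such objective. What remains is that the aim appears in three places, in 5.1 as something to be determined, with nothing behind it.

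A reader might also infer that the gate is a flaw, or that the fit test exists only to discard failures. The documents do not support that. The test also selects the mask size, and requiring a seal before measuring CO2 is defensible, since a leaking mask could understate rebreathing.

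Nor do the documents show that the final report would look the same whatever the pass rate. They do not specify the report's contents. If failures count towards the 100 and are not replaced, a low pass rate would show as fewer children analysed. Figure 1 was not available to this review; it is described as the design algorithm and may count failures, but it is not an analysis plan.

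Finally, a pass proportion would not by itself establish effectiveness. Fit is tested during set exercises, not on the treadmill. The mask's testing to the KN95 protocol is separate from this study (1.1, 7). Exclusion criterion 5 in 3.4 already removes children likely to compromise the fit. This stands and limits what the added outcome may be said to show.

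**Conclusion.** The concern holds in a limited form. If the plan is followed as written, its analyses cannot speak to fit or protection, and the ETCO2 conclusion extends only to children who pass the fit test. The ETCO2 analysis and its sample size do not depend on this point, so it is an inexpensive improvement rather than a threat to the primary result.

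The extent of the gap is unknown, because the documents give neither a pass rate nor a rule on whether fit failures count towards the 100. The intervals in the working illustrate the precision available; they are not evidence that many children will fail.

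**What to change.** Keep the fit gate for the ETCO2 test and make these changes:

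1. Add to 2.3 and 11.2 a descriptive secondary outcome: the proportion of all fit-tested children who reach a fit factor of at least 12.5 in any size, with exact 95% CI. Children who fail stay in this denominator.
2. Summarise the fit factor by mask size and age. Section 11.1 mentions age groups without defining them, so the bands need to be stated.
3. Say in 6.1 b that fit results are recorded for children who fail, which the protocol does not now say, and state whether they count towards the 100.
4. State in 11.2 that the ETCO2 conclusion applies to children who pass.
5. Describe the new outcome as evidence on fit, not as full proof of effectiveness.

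If items 1 and 2 are not adopted, remove effectiveness from the aim in 1.1, 1.2 c and 5.1; editing fewer than all three leaves the mismatch in place.

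The cost is one extra table from a test already performed on each child, plus recording the failures. The downside for the sponsor is that the reported fit rate may be less favourable than hoped.

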6. METHODS AND ASSESSMENTS

6.1. Selection of Test Subjects

a. Screening Visit and Procedures

Pre-test actions

An invitation letter with study information sheet which contains the study's objectives, procedures, risk and benefits will be sent to all subjects aged 7 to 14 years old from the selected schools. Their parents will complete a questionnaire to ascertain the students' general well-being, and to ensure that the appropriate criteria for selection / exclusion are applied. Contact of the designated study team member will be provided for any queries.

Subjects who fulfil the eligibility criteria, whose parents return the Reply form expressing their willingness to participate, will proceed on to the study enrolment.

The total number of eligible students may exceed the stated sample size, in which case the participants will be randomly selected from the pool of qualifying subjects.

b. Study Visit and Procedures

On-site pre-screening

An on-site screening questionnaire will be administered by the study team to check on the participant's current well-being. Informed consent and/or assent if applicable will be obtained.

Mask fit test

Biometric data (gender, age, race, height, and weight) of the subjects will be recorded. De-identified case report form will be used to record data. Each will then undergo a mask fit test to determine the right mask size for the face, and test for leakage by performing the following exercises in sequence, which would take 12 minutes each: normal breathing, deep breathing, turning their heads sideways, up and down, speaking and bending exercise. The fit test will be performed using the Portacount Respirator Fit Tester which indicates the fit factor (ratio of ambient air particle concentration vs. in-mask particle concentrations). A high fit factor will indicate a good seal, and the passing fit factor is 12.5 (8% leakage) based on respirator certification EN 149:2001+A1:2009 FFP2 standards. Should a subject keep failing the fit test despite trying on all the sizes, they will be excluded from the study.

The study

Subjects who pass the fit test will don the monitoring equipment and athletic wear. The physiological monitoring equipment will comprise a pulse oximeter and an ETCO₂ monitor. The pulse oximeter will measure through the use of a finger sensor the percent SPO₂% as well as the HR (beats per minute/bpm). The ETCO₂ measurement (in mmHg) will be made through the use of a nasal cannula and will be used to determine the level of carbon dioxide within the test participant as well as the RR (breaths per minute)¹.

Impact on subject's physiological measurements for different interventions will then be assessed while at rest and on mild exertion.

Determining the parameters for mild exertion

Mild exertion will be achieved using treadmills at speeds that represent realistic children activity levels during play. As the subjects are of varying ages and heights, with correspondingly different levels of physiological reserves, it may not be feasible to assign a specific treadmill speed that would indicate a uniform level of mild exertion.

Based on the known normal resting heart rate of healthy children ages 7-14 years of 70 to 100 beats per minute, this study proposes to keep the actual speed of the treadmill flexible and primarily depend on the subject achieving a target heart rate zone of 50- 60% of maximum heart rate. The rationale for choosing this target is based on studies in adults were achieving a target heart rate zone of 50- 60% of maximum heart rate would yield an exercise intensity of about 40% of maximal oxygen consumption (VO₂max), which is a good indicator of aerobic endurance. For adults, the anaerobic threshold is about 50-60% of VO₂max. There is no literature on VO₂max for children, hence, to be conservative, we have referenced adult threshold and taken 40% of VO₂max as children's normal anaerobic threshold. As such, to attain a stable ETCO₂ during aerobic exercise and before the subject crosses the anaerobic threshold, we aim to keep to 50-60% of predicted maximal heart rate.

The most common method to estimate maximum heart rate within the exercise community is to use the 220 – age formula. This study proposes a more conservative assumption of a maximum heart rate of 194bpm, and a target heart rate zone to be achieved on the treadmill of between 100 – 120bpm. As an additional safety measure, subjects should be encouraged to talk comfortably while on the treadmill. This would indicate that the activity level is appropriate. The child will be led to a target heart rate before 3 minutes of steady state data would be taken. Given the physiological differences between different children, as well as their varying levels of fitness, different times may be required to attain the requisite heart rate for the test.

The test will be carried out in a closed and controlled environment, with temperature range of 26-32 degrees Celsius, relative humidity between 50-80%, and wind speed of <1.5m/s (light breeze).

The general well-being and comfort level of the children whilst wearing the mask will be self-rated using a visual analogue scale at the end of the study period.

The study should take about 50 minutes and will be completed within the same day.

c. Final study Visit:

After the completion of the study procedure, there will be no follow-up or repeat visits required.

d. Post Study Follow up and Procedures

Not applicable

e. *Discontinuation Visit and Procedures*

Subjects may withdraw voluntarily from participation in the study at any time.

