1.2. Rationale and justification for the Study

a. Rationale for the Study Purpose

Haze is a perennial problem in Singapore. There is a need to consider the development of disposable particulate respirator with enhanced safety and comfort specific for use in children.

ST Engineering Innosparks Pte. Ltd. developed a new type of disposable particulate respirator (AIR+ KN95 Mask) that is suitable for use in both adults and children, from ages 7 and above.

b. Rationale for Doses Selected (not applicable)

No drugs are used in the study.

c. Rationale for Study Population

Commercially available disposable masks designed for occupational use are mainly for adults, such masks do not fit well on children. As the masks under study were developed specifically for school-going children, this study is designed to explore whether the new disposable particulate respirator is safe and effective for use in healthy children aged 7 to 14 years of age.

d. Rationale for Study Design

This study entails the study of subjects doing various activities with and without donning on the mask. The baseline results of subjects without donning on the mask will serve as control.

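### Exertion is set by steering heart rate into 100-120 bpm, yet the rise in exertion heart rate with the mask is an analysed outcome; unless each child's treadmill speed is held across conditions, a small rise cannot be read as no mask effect.

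*Combined protocol and SAP*

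**What the plan says.** Section 1.2 d has each child perform activities with and without the mask: "The baseline results of subjects without donning on the mask will serve as control". Section 6.1 b adds that physiological measurements "for different interventions will then be assessed while at rest and on mild exertion".

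For the exertion part, section 6.1 b gives up a fixed treadmill speed because children differ in age, height and physiological reserve. It proposes to "keep the actual speed of the treadmill flexible and primarily depend on the subject achieving a target heart rate zone", and states that "we aim to keep to 50-60% of predicted maximal heart rate". The working figures are "a maximum heart rate of 194bpm, and a target heart rate zone to be achieved on the treadmill of between 100 – 120bpm". On timing: "The child will be led to a target heart rate before 3 minutes of steady state data would be taken". As a safety check, "subjects should be encouraged to talk comfortably while on the treadmill".

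Section 2.3 lists heart rate among the secondary outcomes. Section 11.2 a plans a 95% upper confidence limit for the increase in ETCO2 with the mask, a similar analysis for heart rate, and a repeat of these analyses at rest and on mild exertion.

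The readable text does not say that a child's speed is the same in both conditions, or that speed is recorded. Figure 1, which shows the study design, and the case report form are not visible.

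**The concern.** Heart rate plays two roles. It is the quantity the staff control to produce mild exertion, and it is an outcome whose change with the mask is estimated under that exertion. If the mask raises heart rate at a given workload, a rule that returns heart rate to the same zone removes some or all of that rise by lowering the workload. The upper confidence limit would then look reassuring because of the procedure and not because of the mask.

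At stake is the interpretation of the exertion heart-rate result. If speeds differ between conditions, the exertion ETCO2 increase would also compare unequal work; the documents give no basis for the size or direction of that error. The analyses at rest and the sample size are not affected.

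**Working it through.** **The plan's own figures.** 50% and 60% of 194 bpm are 97.0 and 116.4 bpm. The stated zone of 100-120 bpm is 51.5% to 61.9% of 194. The zone is a rounded version of the 50-60% aim and is 20 bpm wide.

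**Three readings that fit the text.**
- A: the child is led to the zone separately in each condition.
- B: the unmasked speed is carried over and cut in the masked walk only if heart rate would pass 120 bpm.
- C: one speed per child is used in both conditions.

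**Inputs.** From the documents: zone 100-120 bpm (6.1 b), 80 children and a one-sided 5% level (11.1). Assumed, because the documents give no heart-rate effect or SD: true mask effect at equal speed d = 10 bpm (also 5); unmasked heart rate uniform over the zone or part of it; and, where stated, drift of SD 5 bpm in each 3-minute window. The one-sided 95% limit uses t(0.95, 79) = 1.664.

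**Reading A.** Both windows are uniform over 100-120, independently.
- Mean difference 0, whatever d is.
- SD = sqrt(2 × 400/12) = 8.16; upper limit 1.664 × 8.16/sqrt(80) = 1.5 bpm.
- With drift, SD = sqrt(66.7 + 50) = 10.80; upper limit 2.0 bpm.

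**Reading B.** The observed increase is min(d, 120 − unmasked heart rate).
- Uniform over 100-120: mean = d − d²/40 = 10 − 2.5 = 7.5 bpm. The mean square is d² − d³/30 = 66.7, so SD = sqrt(66.7 − 56.25) = 3.23. The upper limit is 8.1 bpm, or 8.9 with drift.
- Uniform over 105-115: room below 120 is uniform over 5-15. Half the children have less than 10 bpm of room (average 7.5) and half show the full 10, so the mean is 0.5 × 7.5 + 0.5 × 10 = 8.75 bpm.
- Uniform over 100-110: every child has at least 10 bpm of room, so the mean is 10 bpm, with no attenuation.

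**Reading C.** The mean is d. With drift, the upper limit at d = 10 is 10 + 1.664 × sqrt(50)/sqrt(80) = 11.3 bpm.

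**How often the upper limit covers the true effect** (simulation, with drift):

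| Reading | Unmasked heart rate | True 5 bpm | True 10 bpm |
|---|---|---|---|
| A | 100-120 | about 1% | about 0% |
| B | 100-120 | about 81% | about 11% |
| B | 105-115 | about 95% | about 55% |
| B | 100-110 | about 95% | about 95% |
| C | any | about 95% | about 95% |

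Reading A fails wherever heart rate sits in the zone. Reading B fails only if unmasked heart rate sits high enough for the mask to push it past 120 bpm.

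**The case against.** The strongest reply is that the reason given for flexible speed concerns differences between children, which fits one speed per child. Nothing suggests changing a child's speed because of the mask, and the sequence of walks would naturally be shown in Figure 1. This stands as far as it goes. A reader might infer that the trial re-sets speed for the mask, or that its exertion heart-rate result is necessarily biased. The documents do not support either: reading C is compatible with the text, and the figure is missing from the copy reviewed. But the text does not require C, and the written rule is a heart-rate target to be reached before data are taken. Even the two exertion windows are inferred, although an increase with the mask on exertion needs a measurement in each condition.

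A second reply is that matching on heart rate is deliberate: section 6.1 b wants a stable ETCO2 below the anaerobic threshold, and comparing ETCO2 at equal relative intensity is a legitimate target. That also stands for ETCO2. It cannot serve for heart rate itself, where matching removes the quantity being estimated. A reader might also infer that the ETCO2 conclusion is biased toward safety; no size or direction can be established from the documents.

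Third, exertion heart rate is one secondary parameter with no margin, and the hypothesis and sample size rest on ETCO2. This limits the weight of the point.

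Finally, holding speed has a safety side. With unmasked heart rate uniform over 100-120, the share passing 120 bpm at a held speed is d/20: 25% if the mask adds 5 bpm and 50% if it adds 10, with a maximum of 130 bpm (130/194 = 67%, above the 60% aim). The remedy therefore needs an upper limit and a lower starting aim.

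**Conclusion.** The concern holds in conditional form. The plan controls exertion through the same variable whose exertion increase it analyses, and no readable text holds a child's speed constant. If the rule is applied in each condition separately, the expected heart-rate increase is about 0 whatever the mask does, and for an assumed true 10 bpm the upper limit is about 2 bpm. If speed is cut only above 120 bpm, the expected increase lies between 7.5 and 10 bpm over the heart-rate ranges considered. If one speed is used, there is no bias. As the plan does not say which applies, a small exertion increase could not be taken as absence of a mask effect.

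The sizes rest on an illustrative mask effect and assumed distributions. If Figure 1 or the case report form fixes speed within the child, the point falls. This is a cheap improvement to the interpretation of a secondary outcome, not a threat to the resting ETCO2 comparison.

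**What to change.** **Section 6.1 b.** Set each child's treadmill speed once, in whichever walk comes first, aiming low in the zone (for example 100-110 bpm), and use the same speed in the other condition. Slow the treadmill if the talk check fails or a pre-stated upper heart-rate limit is passed. Leave the withdrawal criteria (3.5) and replacement rule (3.6) as they are. Record the speed in both windows.

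**Section 11.2 a.** Report the exertion heart-rate and ETCO2 increases as equal-speed contrasts, with the number of children slowed and their speeds. If speed was in fact re-set in each window, report the speed difference and do not interpret the exertion heart-rate increase as a mask effect.

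**Cost.** Some protocol wording and one recorded field; no more children, visits or walks. Exertion would be slightly milder. Some masked children may still pass 120 bpm; when speed is set without the mask at 100-110 bpm, this needs a mask effect above 10 bpm or drift within the window. If one speed per child was always intended, one sentence saying so and the recorded speed are enough.
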